## **XII. Sample size and statistical power calculations**

### **a. Sample size**

The first group includes mechanically ventilated patients admitted to study ICUs during a pragmatic trial of interventions that will be applied at the level of the ICU. Patients will not be approached directly for inclusion in this study. The interventions will be embedded within the electronic health record that is in use at each hospital. The sample size will be determined by the number of eligible patients that are admitted to study ICUs during the study period, which we estimate will be 27 months during the trial monitoring period. An estimated 6000 patients undergo MV annually within 13 ICUs of the 6 hospitals of UPHS. By extrapolating these data to a 27-month enrollment period, excluding one ICU for strategy development and pilot- testing, and excluding a fraction of patients who will meet exclusion criteria specified above, we estimated before the start of the study that approximately 8,000 MV patients would be eligible for inclusion in the trial across the remaining 12 ICUs during the study's intervention period.

At the time of the first interim analysis , based on the rate of accrual during the first 9 months of the trial and with application of more precise exclusion criteria, we found that the number of eligible patients admitted to study ICUs was lower than projected. Therefore, we revised our projects to estimated samples sizes of 5100 for the MITT (primary) population and 6900 for the ITT population.

The second group includes mechanically ventilated patients admitted to study ICUs in the 12 months after intervention phase has been completed. During this observational phase, there will be no experimental interventions. Study ICUs will be free to design and implement processes of care entirely at their discretion. Patients will be included in the analysis if they meet eligibility criteria, which will be identical to those of the first interventional phase of the study. By extrapolating estimated enrollment data to a 12-month enrollment period, we estimate approximately 3,000 MV patients.

### **b. Statistical power calculations**

We estimated the power of pairwise comparisons of any of the intervention groups (Strategy A or B alone or in combination with C – i.e., four separate intervention groups) with the control group. We initially based our power calculations on the following conservative assumptions: sample size of 8,000 episodes across 12 ICUs; an intracluster correlation within ICUs of 0.1; and a baseline mean value of the primary outcome of 45% with a standard deviation of 45% (based on estimates from a retrospective cohort of patients admitted to ICUs in study hospitals during a 6-month period in 2020, including patients with COVID-19). With these assumptions, we estimate that we will have >95% power to detect an increase of 25% in the mean value of the primary outcome (from 45% to 70%), which would approximate the utilization rates of the study ICU with the highest adherence to tidal volume < 6.0ml/kg ideal body weight. This sample size also has >90% power to detect a difference of 20% and nearly 80% power to detect a difference as low as 15% in any pairwise comparisons. Finally, this sample size has 80% power to detect a reduction in in-hospital mortality from an estimated 25% to 16%.

With the new sample size estimates as detailed above, and using the same assumptions for revised power calculations, we estimated that we have at least 97% power to detect an increase of 25% in the mean value of the primary outcome (from 45% to 70%) and greater than 80% power to detect an increase as low as 17% in the mean value of the primary outcome within the MITT population. In addition, the new estimated MITT sample size has approximately 80% power to detect an 11% reduction in hospital mortality from an estimated 25% to 14%.

## **XIII. Data Safety & Monitoring Board (DSMB)**

An important safeguard to protect research participants is the development of a plan for ongoing data and safety monitoring to anticipate, and protect against, any human subjects research concerns that may arise. A convened DSMB comprised noted experts in critical care, palliative care, and biostatistics to guard against the possibility of any unforeseen risks arising during the study. Members of the DSMB will not be involved in the conduct of the trial. Once convened, the DSMB will perform several duties. First, they will review and approve the research protocol and plans for data and safety monitoring prior to the study's implementation. Second, they will evaluate the progress of the trial. This will include assessment of data quality, participant accrual and retention, participant risk versus benefit, and study outcomes. Third, they will make recommendations to ensure that any identified issues are appropriately addressed. The DSMB will meet after 11 months and 20 months (one-third and two-thirds of the way through the trial enrollment.) We will charge DSMB members with using their judgment in simultaneously considering many data points in making decisions about trial design modifications and trial continuation or termination. The PI ([name]), the project manager, and the data analyst ([name]), will participate in all DSMB meetings as non-voting members. The PI, assisted by the project manager, will be responsible for maintaining communication between the DSMB, the IRB, and study sites.

The trial's DSMB members to monitor the scientific conduct of the study are as follows:

- **[name], MSc** Associate Professor of Medicine in the Division of Allergy, Pulmonary and Critical Care Medicine at Vanderbilt University (DSMB Chair)
- **[name]** Assistant Professor of Preventive Medicine and Director of Clinical Research Informatics at the Keck School of Medicine University of Southern California
- **[name]** Professor of Medicine in the Division of Pulmonary and Critical Care

Medicine, Department of Medicine at Johns Hopkins University and Director of the Johns Hopkins Adherence Research Center (JHARC) and the Director of the Cystic Fibrosis Adherence Program

- **[name], MS, PhD** Professor of Biostatistics within the University of California San Francisco Division of Oral Epidemiology & Dental Public Health and Division of Epidemiology and Biostatistics

## **XIV. Safety data and interim analysis**

### **a. Safety monitoring endpoints**

The trial has no plans to stop the trial early for evidence of effectiveness of the implementation strategies because doing so would reduce our power for secondary analyses and analyses of effect modification. We will propose to stop the trial for early evidence of harm based on in-hospital mortality.

### **b. Timing of analysis and adjustment of significance level**

Two interim analyses will be conducted after approximately 9 months and 18 months after trial launch (one-third and two-thirds of the trial duration, respectively) of two study outcomes: (1) fidelity to LPV (primary outcome, as specified above), and (2) in-hospital mortality. All interim analyses will be performed at the level of an episode of mechanical ventilation. For the open portion of the DSMB meeting, we will summarize data for the entire study population in aggregate, including patient characteristics, key patient outcomes, and the primary study outcome (percentage of time during the first 72h of MV in the ICU that the patient has tidal volume less than or equal to 6.5cc/kg IBW). We will also report adverse event rates among in aggregate.

To evaluate mortality by group, we will first report unadjusted mortality rates by group, and then proceed in a stepwise fashion with up to three risk-adjusted models:

- Model 1: We will use a generalized linear mixed effects model to estimate unadjusted mortality accounting for design issues; that is, including a random effect for ICU, a fixed effect for study group assignment, and a fixed effect for step (to account for potential confounding from calendar time).
- Model 2: We will use a generalized linear mixed effects model to preliminarily test whether study group assignment is associated with mortality after risk adjustment. As in the above model, we will include a random effect for ICU, a fixed effect for study group assignment, and a fixed effect for step (to account for potential confounding from calendar time). Given variability in case mix, we will also include the following covariates for risk adjustment: age, sex, race, source of admission to the hospital, Elixsauser score and LAPS2 score on the day of study enrollment.
- Model 3: If in the risk-adjusted mixed effects model we find an estimated risk difference for mortality of greater than or equal to 5% at a significance level of  $p<0.2$ , where either intervention group has higher mortality compared to the control group, then we will proceed with further analyses. Because interim analyses of accumulating data in a clinical trial can inflate type I error, we will use a flexible spending function. Specifically, we will calculate a Lan-DeMets spending function using O'Brien-Fleming boundaries to preserve the overall significance level of 0.05. The interim tests will use one-sided significance levels of 0.0007 and 0.0161. Final analyses will be conducted at a significance level of 0.0451, preserving a trial-wide Type I error rate of 0.05.

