8.1. Adverse Events and Unanticipated Problems

The study team will be responsible for identifying and reporting all serious adverse events, protocol deviations/violations, and unanticipated problems to the IRB, DSMB, and funding agency promptly, as appropriate. In order for the PI to remain blinded, expert critical care clinicians (attending physician, fellow physician, or advanced practice provider) trained by PI [name] will lead adverse event monitoring and reporting, with the support of the project manager. We will proactively perform surveillance of three adverse events – life-threatening acidemia, and death or cardiac arrest within 24 hours of trial enrollment. Adverse events possibly or likely related to the intervention will be reported immediately to the Data and Safety Monitoring Board (DSMB, see below) within 7 days of occurrence, if fatal or life-threatening. Unanticipated problems will be reported to DSMB within 14 days of identification.

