8.3. Interim Analyses

The trial will be monitored routinely for issues of data quality and study conduct (including participant enrollment and technical issues with EHR order sets) via monthly data extraction and analysis by our research team's data manager, [name]. We will conduct two interim analyses – after approximately 9 months and 18 months (one-third and two-thirds of the trial duration, respectively) – of two study outcomes: (1) fidelity to LPV (primary outcome, as specified above), and (2) in-hospital mortality.

We do not plan to stop the trial early for evidence of effectiveness of the implementation strategies because doing so would reduce our power for secondary analyses and analyses of effect modification. We will propose to stop the trial for early evidence of harm based on in-hospital mortality.

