**Table 2 Secondary outcome measures**

| Implementation Outcomes  | Variable coding | Definition  |
|---|------------------------|--|
| 
 
Total duration of exposure to tidal volume >8 cc/kg and >10 cc/kg IBW
 
 | Continuous             | In hours; exclude time on minimal settings; report for first 72h after enrollment and for entire duration of MV episode within a study ICU   |
| 
 
Initial tidal volume administered
 
   | Continuous             | In cc/kg IBW; exclude time on minimal settings; report the first documented tidal volume at or after the time of enrollment  |
| 
 
Plateau pressure (Pplat) >30cm H2O at time 0 and time 24h
 
                | Binary                 | Time 0 is the earliest measure between 0 and 6h; time 24 is the measure between 18h and 30h that is closest to 24h and earliest if there are two measures of the exact same distance from 24h (e.g., one before and one after) |
| Effectiveness Outcomes   |                        |  |
| 
 
Hospital mortality
 
  | Binary                 | Vital status at hospital discharge   |
| 
 
Hospital discharge disposition
 
  | Categorical            | To be collapsed into 4-6 categories  |
| 
 
Duration of MV
 
  | Continuous             | From time of enrollment to end of MV in study ICUs, up to 30 days  |
| 
 
ICU length of stay
 
  | Continuous             | From time of enrollment to end of admission to enrolling ICU, up to 30 days  |
| 
 
Hospital length of stay
 
   | Continuous             | From time of enrollment to time of hospital discharge, up to 30 days   |
| Potential Adverse Effects  |                        |  |
| 
 
Early deep sedation
 
   | Continuous             | Proportion of time during the first 72 hours of mechanical ventilation that patients were alive, in the ICU, and with Richmond Agitation-Sedation Scale (RASS) of -3 to -5   |

|  |            |  |
|--|------------|--|
| • Average sedation intensity within the first 72 hours                           | Continuous | Average RASS value, weighted by duration of time at that value   |

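### No between-group comparison is specified for two of the three harms under active surveillance: life-threatening acidemia and cardiac arrest

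*SAP*

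**What the plan says.** **Surveillance.** Protocol 8.1 states: "We will proactively perform surveillance of three adverse events – life-threatening acidemia, and death or cardiac arrest within 24 hours of trial enrollment". The same section sets the route to the board: "Adverse events possibly or likely related to the intervention will be reported immediately to the Data and Safety Monitoring Board", within 7 days if fatal or life-threatening.

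**Interim looks.** Protocol 8.3 plans two interim analyses "of two study outcomes: (1) fidelity to LPV (primary outcome, as specified above), and (2) in-hospital mortality", and SAP XIV.b repeats this. SAP XIV.b then describes the meeting: "For the open portion of the DSMB meeting, we will summarize data for the entire study population in aggregate". The sentence on adverse event rates, "We will also report adverse event rates among in aggregate", closes that paragraph. The by-group text comes next and opens with "To evaluate mortality by group, we will first report unadjusted mortality rates by group". The three models that follow are all for mortality. The harm criterion in protocol 8.3 and SAP XIV.a is in-hospital mortality only.

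**Final analysis.** SAP X says that the adverse effects to be analysed are those in Table 2. Under "Potential Adverse Effects" that table has three rows, all based on the RASS sedation scale. Protocol 3.9.2 lists the same three. The protocol summary gives a different list (sedative doses and days of acute brain dysfunction), but it too omits acidemia and cardiac arrest.

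**The concern.** The trial selected these events as the ones worth looking for, and it is meant to raise the use of low tidal volumes. Protocol 6.1 itself lists adverse consequences of that increase as a potential risk, and the consent waiver rests on risk being minimal. The natural evidence on that point is the rate of each surveilled event in control time against strategy time. If no such comparison is specified, an excess of acidemia or arrest that does not kill could go unseen in the planned analyses, and the trial could not support a safety conclusion on those two harms.

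**Working it through.** The documents state no rate, sample size or power for acidemia or cardiac arrest, so there is no figure of theirs to reproduce. The check is to trace each surveilled event through the plan.

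| Surveilled event | Interim, by group | Harm criterion | Final, by group |
|---|---|---|---|
| Death | Yes, as in-hospital mortality (SAP XIV.b) | Yes (protocol 8.3, SAP XIV.a) | Yes, as hospital mortality (SAP Table 2) |
| Life-threatening acidemia | None specified | None | None specified |
| Cardiac arrest | None specified | None | None specified |

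Death within 24 hours has no separate analysis, but in-hospital mortality covers it. Three other routes might fill the two empty rows.

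**1. Case reports by relatedness.** An event in control time cannot be related to a strategy that is not yet in place. Counts of related events therefore have no control-period counterpart. The reviewing clinician may also be unblinded to assignment as needed (protocol 3.6), so knowledge of it can colour the judgement. Both events have many causes in ventilated patients, so single cases are hard to attribute.

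**2. The pooled rate.** Assume 3-month steps. Adoption then falls after months 3, 6, 9, 12, 15 and 18, which fits the stated layout: 18 + 6 months before Strategy C + 3 months combined = 27. Assume also even accrual per ICU-month. At month 18:
- Control ICU-months: 2 × (3 + 6 + 9 + 12 + 15 + 18) = 126
- All ICU-months: 12 × 18 = 216
- Strategy ICU-months: 216 − 126 = 90

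Pooled rate = (126 × control rate + 90 × strategy rate) / 216. For assumed rates:
- 1% doubling to 2%: (126 + 180)/216 = 1.4%
- 3% doubling to 6%: (378 + 540)/216 = 4.25%
- 5% doubling to 10%: (630 + 900)/216 = 7.1%

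Each pooled figure is equally compatible with the same rate in every group. Pooling is right for an open session, but it cannot replace a comparison.

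**3. Mortality as a proxy.** The expected rise in mortality from an excess of d points, of which a fraction f die, is d × f. With f = 0 nothing appears. With an assumed d = 3 and f = 1 the expected rise is 3 points, below the 5-point estimated difference (with p<0.2) that SAP XIV.b requires before Model 3. Mortality by group would still be displayed, but it would not identify either event.

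**Precision if the comparison is added.** Take the projected MITT size of 5,100 and the same step layout over 27 months.
- Control share: mean of the six adoption months / 27 = 10.5/27 = 38.9%, about 1,983 episodes
- Strategy A alone: half of 6/27 = 11.1%, about 567 episodes
- Events at assumed rates of 1% and 2%: 1,983 × 0.01 ≈ 20 against 567 × 0.02 ≈ 11
- Events at assumed rates of 5% and 10%: 1,983 × 0.05 ≈ 99 against 567 × 0.10 ≈ 57

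At the low end the comparison would be imprecise even before allowing for clustering and calendar time. It should be labelled descriptive.

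**The case against.** The strongest reply has four parts.

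**The open-session sentence is sound.** The PI and the data analyst attend DSMB meetings and are to stay blinded, so pooled reporting there is what the plan needs. This stands. A reader might infer from the word aggregate that this sentence is the flaw; it is not. The gap lies in what the by-group steps and Table 2 leave out.

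**Silence is not a prohibition.** The adverse event content of the closed session is not described. An unblinded project manager communicates with the board, which approves the monitoring plan and weighs risk against benefit. No text limits the final report to Table 2. SAP Appendix B, and what appears to be the opening of protocol 6.2, were not in the text available for this review. This also stands. A reader might infer that the trial never compares these harms, or that the DSMB could not learn of an excess; neither can be shown. What can be shown is that no such comparison is specified in the available text.

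**Any effect size would be invented.** This stands too. It is tempting to compute a test statistic from assumed rates. Such a figure would ignore clustering and time, which the SAP's own model includes, and would pool strategies that the plan compares separately.

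**The fix may need more than wording.** The available text gives no threshold for life-threatening acidemia, does not say how cases are found, and leaves unclear whether the 24-hour window applies to acidemia. This is a fair limit on the cost estimate. It does not remove the gap.

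**Conclusion.** The point holds in a limited form. Two of the three surveilled harms have no specified between-group comparison, interim or final, in the available text. This is more than a missing detail, because the SAP names the adverse effects that it will analyse and these two are not among them. An excess of non-fatal acidemia or arrest under a strategy would not be shown by any specified analysis, and relatedness reports cannot supply the comparator.

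The conclusion rests on the text alone and needs no assumed rate. The pooled rates, the mortality ceiling and the event counts above are illustrations under stated assumptions. The plan should be changed on this point, but mortality monitoring and the open-session reporting are not called into question by it.

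**What to change.** Add life-threatening acidemia and cardiac arrest to SAP Table 2 under potential adverse effects.
- Write the surveillance definition already in use into the table, and state the time window for each event. Apply the same definition, EHR ascertainment and window in control and intervention time.
- Report counts and rates by study group. Give an estimate and confidence interval from the binary model in SAP X.a (ICU random effect, step fixed effect), labelled descriptive. If events are too few for the model to fit, report counts and rates alone.
- Show the same counts by group, beside mortality, in the closed DSMB report at any remaining look. Keep the open session pooled.

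SAP XIV.c places trial completion in May 2023, so the interim part may no longer apply. The Table 2 change still serves the final report.

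The cost is SAP wording and two binary models. No new data are needed if surveillance already ran identically in control time; if it did not, control-period events must be extracted from the EHR under the same definition. The downside is two more safety comparisons without multiplicity adjustment, imprecise if events are rare.

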### **c. Timing of final analysis**

Final analysis of the trial monitoring period will occur following completion of the trial in May 2023.

### **d. Person performing analysis**

Statistical analysis will be performed by the trial's data analyst who will be blinded to trial arm.

[figure not shown]
All other members of the investigative team except the data manager and project manager will remain blinded to treatment assignments and facilities for the analysis. The trial's data manager and project manager will be the only people who knows the treatment assignments during the trial's conduct. Neither the data manager or project manager will be involved in developing or modifying the statistical analysis plan or in the actual analyses.

## Appendix A

### Schematic diagram for INPUT Trial

The schematic diagram above illustrates the roll-out of three implementation strategies in the stepped-wedge design: (1) a default order panel, (2) an accountable justification order panel, and (3) an accountable justification flowsheet strategy that targets respiratory therapists.
